9.1. Efficacy Assessments

9.1.1. Primary Efficacy Assessment – Hyperphagia Questionnaire for Clinical Trials

The HQ-CT is a validated tool developed specifically for PWS, to capture observations of problematic behaviors related to food. It was adapted in a rigorous and systematic manner for use in clinical trials (HQ for Clinical Trials or HQ-CT) by Zafgen, Inc. for the ZAF-312 clinical trial, and donated to the Foundation for Prader-Willi Research in 2016 to facilitate its use across clinical trials for PWS. It consists of 9 items, with a 2-week recall period. The scale provides a composite value from 9 questions, each rated on a scale of zero to 4 units (total range of score of zero to 36; [Fehnel et al. 2015](#)).

9.1.2. Secondary Efficacy Assessment – Caregiver Global Impression of Change

Caregiver Global Impression of Change (CGIC) is a single-item question rated on a 0 to 7 scale directed at the caregiver asking them to assess overall improvement in patients with PWS. This tool was adapted by Zafgen, Inc. for the ZAF-312 clinical trials.

9.2. Adverse Events

A clinical trial AE is any untoward medical event associated with the use of a drug or drug delivery system in humans, whether or not it is considered related to that drug or drug delivery system.

The sponsor has standards for reporting AEs that are to be followed regardless of applicable regulatory requirements that may be less stringent.

Investigators are responsible for monitoring the safety of patients who have entered this study and for alerting sponsor or its designee to any event that seems unusual, even if this event may be considered an unanticipated benefit to the patient.

The investigator is responsible for the appropriate medical care of patients during the study.

Investigators must document their review of each laboratory safety report.

The investigator remains responsible for following, through an appropriate healthcare option, AEs that are serious or otherwise medically important, considered related to the study drug or the study, or that caused them to discontinue the study drug before completing the study. The patient should be followed until the event resolves, stabilizes with appropriate diagnostic evaluation, or is reasonably explained. The frequency of follow-up evaluations of the AE is left to the discretion of the investigator.

Lack of drug effect is not an AE in clinical studies, because the purpose of the clinical study is to establish treatment effect.

After the ICF is signed, study site personnel will record via EDC the occurrence and nature of each patient's preexisting conditions, including clinically significant signs and symptoms of the disease under treatment in the study. In addition, site personnel will record any change in the condition(s) and any new conditions as AEs. Investigators should record their assessment of the potential relatedness of each AE to protocol procedure or study treatment via EDC.

The investigator will interpret and document whether or not an AE has a reasonable possibility of being related to study treatment, or a study procedure, taking into account the disease, concomitant treatment, or pathologies.

A "reasonable possibility" means that there is a cause and effect relationship between the study drug, study device, and/or study procedure and the AE.

The investigator answers yes/no when making this assessment.

Ratings of AEs will be based on the following 3-point severity scale:

Mild	Awareness of sign or symptom, but it is easily tolerated; does not interfere with daily activities
Moderate	Discomfort enough to slightly disrupt daily activities. Medical intervention and/or close follow-up may be considered
Severe	Incapacitating with complete disruption of daily activities. Medical intervention and/or close follow-up likely.

Planned surgeries and nonsurgical interventions should not be reported as AEs unless the underlying medical condition has worsened during the course of the study.

If a patient's study drug is discontinued as a result of an AE, study site personnel must report this to sponsor or its designee via EDC, clarifying if possible, the circumstances leading to any dosage modifications, or discontinuations of treatment.

9.2.1. Serious Adverse Events

Study site personnel must alert the sponsor or its designee of any SAE within 24 hours of investigator awareness of the event via a sponsor-approved method. Serious adverse event reporting to the sponsor begins after the patient has signed the ICF.

If alerts are issued via telephone, they are to be immediately followed with official notification on study-specific SAE forms. This 24-hour notification requirement refers to the initial SAE information and all follow-up SAE information. Patients with a serious hepatic AE should have additional data collected using the EDC (Section 9.4.5.1).

An SAE is any AE from this study that results in 1 of the following outcomes:

- death
- initial or prolonged inpatient hospitalization
- a life-threatening experience (i.e., immediate risk of dying)
- persistent or significant disability/incapacity
- congenital anomaly/birth defect
- important medical events that may not be immediately life-threatening or result in death or hospitalization but may jeopardize the patient or may require intervention to prevent one of the other outcomes listed in the definition above. Examples of such medical events include allergic bronchospasm requiring intensive treatment in an emergency room or at home, blood dyscrasias or convulsions that do not result in inpatient hospitalization, or the development of drug dependency or drug abuse.

Previously planned (prior to the signing of ICF) surgeries should not be reported as SAEs unless the underlying medical condition has worsened during the course of the study.

The following terms will be utilized to assess the relationship of the SAE to administration of study treatment:

- **Probably related:** a direct cause and effect relationship between the study treatment and the AE is likely.
- **Possibly related:** a cause and effect relationship between the study treatment and the AE has not been demonstrated at this time and is not probable, but is also not impossible.
- **Unlikely:** likely to be due to another etiology.
- **Not related:** without question, the AE is definitely not associated with the study treatment.

Investigators are not obligated to actively seek AEs or SAEs in patients once they have discontinued and/or completed the study. Serious adverse events occurring after a patient has taken the last dose of study drug will be collected for 30 days after the last dose of the study drug. However, if the investigator learns of any SAE, including a death, at any time after a patient has been discharged from the study, and he/she considers the event reasonably possibly related to the study treatment or study participation, the investigator must promptly notify the sponsor.

Pregnancy (during maternal or paternal exposure to study treatment) does not meet the definition of an AE. However, to fulfill regulatory requirements any pregnancy should be reported following the SAE process to collect data on the outcome for both mother and fetus.

The medical representative of the sponsor will monitor safety data throughout the course of the study. The sponsor and/or its designee will review SAEs within appropriate timeframes to meet reporting obligations imposed by regulatory authorities. All serious and unexpected AEs for this study will be reported to regulatory authorities in accordance with local laws, directives, and regulations.

9.2.1.1. Suspected Unexpected Serious Adverse Reactions

Suspected unexpected serious adverse reactions (SUSARs) are serious events that are not listed in the IB ([GLWL-01 2017](#)) and that the investigator identifies as related to the study drug or procedure. The sponsor has procedures that will be followed for identifying, recording, and expedited reporting of SUSARs that are consistent with global regulations and the associated detailed guidance.

9.2.2. Complaint Handling

The sponsor collects product complaints on study drugs and drug delivery systems used in clinical studies in order to ensure the safety of study participants, monitor quality, and to facilitate process and product improvements.

Patients will be instructed to contact the investigator as soon as possible if he or she has a complaint or problem with the study drug so that the situation can be assessed.

9.3. Treatment of Overdose

Refer to the IB ([GLWL-01 2017](#)).

9.4. Safety

9.4.1. Electrocardiograms

For each patient, 12-lead ECG recordings and ECG extractions should be performed according to the Schedule of Activities (Section 2).

Patients must be in a quiet environment without significant external stimulation (e.g., television or internet), must be in supine position for at least 5 to 10 minutes before the specified ECG collection time, and must remain supine but awake during ECG collection and for at least 5 minutes afterward. Patients are to be encouraged to remain still if possible during this time.

Any clinically significant findings from ECGs that result in a diagnosis and that occur after the patient receives the first dose of the study drug should be reported to the sponsor or its designee as an AE via EDC.

9.4.2. Vital Signs

For each patient, vital sign measurements should be conducted according to the Schedule of Activities (Section 2). Triplicate measurements (collected approximately 1 minute apart) of sitting BP, and single pulse and temperature, will be measured.

Any clinically significant findings from vital sign measurements that result in a diagnosis and that occur after the patient receives the first dose of study drug should be reported to the sponsor or its designee as an AE via electronic data entry.

9.4.3. Laboratory Tests

For each patient, laboratory tests detailed in [Appendix 2](#) should be conducted according to the Schedule of Activities (Section 2). The blood samples should be collected in a fasted state.

With the exception of laboratory test results that may unblind the study, sponsor or its designee will provide the investigator with the results of laboratory tests analyzed by a central vendor, if a central vendor is used for the clinical trial.

Any clinically significant findings from laboratory tests that result in a diagnosis and that occur after the patient receives the first dose of study drug should be reported to the sponsor or its designee as an AE via electronic data entry.

9.4.4. Columbia Suicide-Severity Rating Scale

Columbia Suicide-Severity Rating Scale: A scale that captures the occurrence, severity, and frequency of suicidal ideation and/or behavior during the assessment period. The scale includes suggested questions to solicit the type of information needed to determine if suicidal ideation and/or behavior occurred. The C-SSRS is administered by an appropriately trained healthcare professional with at least 1 year of patient care/clinical experience or some or all of the patients may have these data solicited through interactive web-response system or electronic patient reported outcome technology. This tool was developed by the National Institute of Mental Health trial group (Treatment of Adolescent Suicide Attempters) for the purpose of being a counterpart to the C-CASA categorization of suicidal events.

The nonleading AE collection should occur prior to the collection of the C-SSRS. If a suicide-related event is discovered during the C-SSRS but was not captured during the nonleading AE collection, sites should not change the AE form. If an event is serious or leads to discontinuation, this is an exception where the SAE and/or AE leading to discontinuation should be included on the AE form and the process for reporting SAEs should be followed.

Terms captured by the use of the C-SSRS can be mapped to Columbia Classification Algorithm for Suicide Assessment ([Posner et al. 2007](#)) to facilitate future pooling of data.

The first time the scale is administered in this study, the C-SSRS “Lifetime/Recent-Clinical” version will be used, and the findings will constitute the baseline assessment. The “Since Last Visit-Clinical” version will be used for all subsequent assessments. If a suicide-related thought or behavior is identified at any time during the study, a thorough evaluation will be performed by a study physician, and appropriate medical care will be provided. If, based on administration of

the C-SSRS, it is determined that suicide-related behaviors have occurred, then the additional information will be collected to allow for a more complete assessment of these behaviors.

9.4.5. Safety Monitoring

The sponsor and designee will periodically review evolving aggregate safety data within the study using appropriate methods.

9.4.5.1. Hepatic Safety Monitoring

If a study patient experiences elevated ALT ≥ 3 X ULN, ALP ≥ 2 X ULN, or elevated TBL ≥ 2 X ULN, liver tests ([Appendix 4](#)) should be repeated within 3 to 5 days including ALT, AST, ALP, TBL, direct bilirubin, gamma-glutamyl transferase, and creatine kinase to confirm the abnormality and to determine if it is increasing or decreasing. If the abnormality persists or worsens, clinical and laboratory monitoring should be initiated by the investigator and in consultation with the study medical monitor. Monitoring of ALT, AST, TBL, and ALP should continue until levels normalize or return to approximate baseline levels.

Hepatic Safety Data Collection

Additional safety data should be collected via the electronic data entry if 1 or more of the following conditions occur:

- elevation of serum ALT to ≥ 5 X ULN on 2 or more consecutive blood tests
- elevation of serum TBL to ≥ 2 X ULN (except for cases of known Gilbert's syndrome)
- elevation of serum ALP to ≥ 2 X ULN on 2 or more consecutive blood tests
- patient discontinued from treatment due to a hepatic event or abnormality of liver tests
- hepatic event considered to be an SAE

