6.2. Exclusion Criteria

Patients will be excluded from study enrollment if they meet any of the following criteria at screening:

9. Are Eli Lilly and Company, GLWL Research Inc. (sponsor hereafter), contract research organization employees, investigator or site personnel directly affiliated with this study and their immediate families. Immediate family is defined as a spouse, parent, child or sibling, whether biological or legally adopted.
10. Are currently enrolled in any other clinical trial involving a study drug or off-label use of a drug or device, or any other type of medical research judged not to be scientifically or medically compatible with this study.
11. Participated in a clinical trial within 30 days (defined as last dose of study drug), prior to the GLWL-PWS first dose.
12. Are currently living in a group home for more than 50% of the time.
13. Have a HQ-CT total score at Visit 3 <13.
14. Have clinical laboratory test results outside normal reference range, or any clinically significant laboratory abnormality, that in the judgment of the investigator, indicates a medical problem that would preclude study participation. Values for aspartate aminotransferase (AST)/alanine aminotransferase (ALT)/gamma-glutamyl transferase (GGT)/alkaline phosphatase (ALP) >3X upper limit of normal (ULN).
15. Have an estimated glomerular filtration rate <60 mL/minute/1.73 m². Have macroalbuminuria (defined as spot urine albumin to creatinine ratio of >300 µg/mg) or hematuria.
16. Are hypertensive (defined as sitting systolic BP ≥140 mmHg and diastolic BP ≥90 mmHg) on or off medications for the treatment of hypertension. Blood pressure may be re-tested up to 2 additional times, under well-rested conditions.

17. In addition to conditions described below, have a history or presence of any other medical illness including but not limited to any autoimmune disorder, cardiovascular, hepatic, respiratory, hematological, or uncontrolled neurological disease.

- a. Have a history of clinically overt uncontrolled or untreated endocrine illness such as growth hormone insufficiency, adrenal gland, or thyroid illness.

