7.8. Treatment after the End of the Study

Not applicable.

8. Discontinuation Criteria

Patient participation in the study may be discontinued for any of the following reasons:

- Enrollment in any other clinical study involving any study drug or enrollment in any other type of medical research judged not to be scientifically or medically compatible with this study.
- **Investigator's decision:** the investigator decides that the patient should be discontinued from the study.
- **Patient's/caregiver's decision:** the patient or caregiver requests to be discontinued from the study.
- **Sponsor's decision:** GLWL stops the study or stops the patient's participation in the study for medical, safety, regulatory, or other reasons consistent with applicable laws, regulations, and GCP.
- **Adverse event:** any SAE or a significant change in a laboratory value occurs that merits the study drug being discontinued and necessitates appropriate measures being taken. In this case, the sponsor is to be notified immediately.
- **Hepatic event or liver test abnormality:** Patients who are discontinued from using study drug due to a hepatic event or liver test abnormality should have additional hepatic safety data collected via electronic data entry.

Discontinuation of the study drug for abnormal liver test results **should be** considered by the investigator when a patient meets 1 of the following conditions after consultation with the sponsor medical representative:

- ALT or AST >5X ULN
- ALT or AST >3X ULN along with 1 of the following criteria:
 - sustained for more than 2 weeks or
 - total bilirubin level (TBL) >2X ULN or
 - prothrombin time >1.5X ULN or
 - the appearance of fatigue, nausea, vomiting, right upper-quadrant pain or tenderness, fever, rash, and/or eosinophilia (>5%)
- ALP >3X ULN
- ALP >2.5X ULN and TBL >2X ULN
- ALP >2.5X ULN with the appearance of fatigue, nausea, vomiting, right upper-quadrant pain or tenderness, fever, rash, and/or eosinophilia (>5%)
- Marked prolongation of the QT/QTc interval >500 ms or >60 ms over baseline, judged medically significant following repeat ECG after 5 minutes of rest from the initial ECG.

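### A raised AST does not trigger the 3-to-5-day liver recheck, although the protocol treats AST and ALT alike as grounds to consider stopping study drug

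*Protocol*

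**What the plan says.** Protocol Section 9.4.5.1 (Hepatic Safety Monitoring) calls for a repeat of liver tests within 3 to 5 days when a patient has "elevated ALT ≥ 3 X ULN, ALP ≥ 2 X ULN, or elevated TBL ≥ 2 X ULN". AST does not start the repeat. It is measured once the repeat has been started, in a panel "including ALT, AST, ALP, TBL, direct bilirubin, gamma-glutamyl transferase, and creatine kinase", and it is among the tests then followed until they settle.

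Protocol Section 8 (Discontinuation Criteria) sets two transaminase conditions. One is "ALT or AST >5X ULN". The other is "ALT or AST >3X ULN along with 1 of the following criteria", and the first criterion in that list reads "sustained for more than 2 weeks or". The alternatives are raised bilirubin, prolonged prothrombin time, or listed symptoms or eosinophilia. Meeting a condition does not stop treatment automatically. Stopping is to be "considered by the investigator when a patient meets 1 of the following conditions after consultation with the sponsor medical representative".

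Section 9.4.5.1 also lists when extra hepatic data are collected. Its transaminase trigger is "elevation of serum ALT to ≥ 5 X ULN on 2 or more consecutive blood tests". Two of its other triggers name no analyte: discontinuation for a hepatic reason, and a serious hepatic event.

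The Schedule of Activities places clinical chemistry, which includes AST (Appendix 2), at Visits 1, 3, 4, 5, 8, 9 and 10 and at early termination.

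**The concern.** A recheck rule exists to supply the second value on which a decision about study drug can rest. Here the decision rule covers both transaminases and the recheck rule covers only one. The mismatch matters most for the persistence criterion, which cannot be judged without a later value. If a patient's only abnormality is AST, nothing in the protocol requires that value while the patient is still taking drug. Two sites could also handle the same result differently, one retesting within days and the other waiting for the next scheduled visit. At stake is the safety of an individual patient for the rest of one dosing phase.

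**Working it through.** The protocol states no figure to reproduce. The check sets the rules side by side and takes the gaps from the visit schedule.

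**1. The rules compared**

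| Step | ALT | AST |
|---|---|---|
| Consider stopping (Section 8) | >5X, or >3X plus a criterion | the same |
| Triggers the 3-to-5-day repeat (9.4.5.1) | ≥3X | no |
| Measured in the repeat | yes | yes |
| Followed if the abnormality persists | yes | yes, once a repeat has been triggered |
| Laboratory trigger for extra data | ≥5X on 2 tests | no |
| Extra data after hepatic discontinuation or SAE | yes | yes |

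No other section adds a required AST recheck.

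**2. Who falls in the gap**

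- AST above 5X meets a Section 8 condition on a single result.
- AST above 3X with bilirubin above 2X, listed symptoms or eosinophilia also meets one on a single visit.
- If ALT is at least 3X, or ALP or TBL at least 2X, the repeat is triggered anyway and AST is measured with it.
- What remains is AST above 3X and up to 5X, with ALT below 3X, ALP and TBL below 2X, and no symptoms.

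**3. How long the gap lasts, on nominal days**

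- Period 1: Visit 4 to Visit 5 = 42 − 21 = 21 days.
- Period 2: Visit 9 to Visit 10 = 112 − 91 = 21 days.

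**4. How long across the windows**

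Schedule footnote b fixes the end-of-phase visit 28 days after the first double-blind dose.

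- Visit 3 falls on Day 12 to 16 (14 ± 2) and Visit 4 on Day 19 to 23 (21 ± 2).
- Visit 4 therefore falls between phase day 19 − 16 = 3 and phase day 23 − 12 = 11.
- The gap to the end of the phase is 28 − 11 = 17 days to 28 − 3 = 25 days.
- Visits 8 and 9 (Days 82 to 86 and 89 to 93) give the same range: 89 − 86 = 3 and 93 − 82 = 11.

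Even the shortest gap exceeds 14 days. A rise could therefore last more than 2 weeks during dosing with no required test to show it.

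**5. What adding AST to the trigger would supply**

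It gives a value 3 to 5 days after the first raised one. That confirms or refutes the rise but is too early to show persistence beyond 2 weeks. The follow-up that starts after a confirmed abnormality has no stated interval, so it does not guarantee a later value before dosing ends. If retests then run weekly from the repeat, values fall 10 to 12 and 17 to 19 days after the first raised result. On the nominal schedule the last of these comes 21 − 19 = 2 to 21 − 17 = 4 days before the end-of-phase visit. When the gap is only 17 days, it comes no earlier than that visit.

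**The case against.** The strongest reply is that triggering on ALT is a defensible choice. AST can rise for reasons outside the liver, and the protocol still measures AST at every scheduled chemistry visit. Several safeguards would bring a rise to attention:

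- investigators must document their review of each laboratory report and follow medically important events (Section 9.2);
- the sponsor's medical representative monitors safety data throughout (Section 9.2.1);
- Appendices 4 and 5 allow unscheduled hepatic tests.

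Section 3.3 also reports no clinically significant safety concern at doses up to 600 mg twice daily for 28 days, above the dose used here.

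Much of this stands. An AST rise would be seen, and a careful investigator could retest it. But each safeguard leaves the timing of a retest to choice, whereas Section 9.4.5.1 makes a prompt repeat a rule for ALT. Doubt about the source of an AST rise is itself a reason to repeat it, because the repeat panel includes creatine kinase.

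Four stronger readings are tempting and are not supported:

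- *That extra hepatic data collection ignores AST.* Hepatic discontinuations and serious hepatic events trigger it whichever analyte was raised. Only repeated AST at 5X or more with neither of these is missed.
- *That Section 8 makes an AST rise a stopping rule.* It sets conditions for considering a stop, after consultation.
- *That a particular number of doses would be spared.* This would need a later value at a fixed time, an immediate result and a decision to stop. The documents guarantee none of these, even for ALT.
- *That the shared 3X entry limit shows that equal on-study triggers were intended.* Exclusion 14 applies that limit to GGT and ALP too. GGT is not an on-study trigger, and ALP is rechecked from 2X.

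**Conclusion.** The inconsistency is real and narrow. A patient with an isolated, symptom-free AST rise above 3X and up to 5X ULN at Visit 4 or Visit 9 has no required second value for a nominal 21 days (17 to 25 across the windows), by which time dosing has ended. The same rise in ALT would be repeated within 3 to 5 days.

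Severity is minor. The documents give no frequency for isolated AST rises. SAP Section 2.9 anticipates 19 patients, and only one of each patient's two double-blind phases is active drug, so few or no patients may be affected. Efficacy and power are not touched.

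The conclusion assumes that chemistry is drawn at Visits 4 and 9, as the protocol's Schedule of Activities states (SAP Section 7.3 lists only phase Days 0 and 28). It also assumes that the investigator does not choose to retest sooner.

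**What to change.** 1. In Section 9.4.5.1, change the transaminase recheck trigger to ALT or AST at 3X ULN or more. This gives a prompt confirmatory value with creatine kinase and, if the rise persists, starts the monitoring already described there.
2. Add that a confirmed ALT or AST above 3X ULN is retested at least weekly while dosing continues. Without a stated interval, the 2-week criterion in Section 8 may not be assessable before dosing ends. If the first raised value comes late in the visit window, one draw should be timed for day 15 or 16 after it.
3. Optional, for consistency only: add AST to the 5X data-collection trigger.

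The cost is protocol wording and a few unscheduled draws in affected patients. Some draws will follow AST rises that are not hepatic. Appendix 5 already foresees hepatic monitoring samples of 3 to 30 mL, against a planned 154 mL per patient (3/154 = 1.9% to 30/154 = 19.5%). No patients or scheduled visits are added. If dosing has finished, carry the wording into the next protocol for this drug.
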